8.2.2 Selection and Number of Sites

All four hospitals in BOAO Pilot Zone providing treatment of sotorasib will be included unless demonstrated operationally unfeasible (eg, Ruijin Hainan Hospital, BOAO Super Hospital, BOAO Hengda Hospital, and BOAO Future Hospital).

The Hong Kong SAR CDARS database covering residents in Hong Kong SAR will be used to extract data of sotorasib treated patients. Details of data sources are provided in Section 8.4.

8.2.3 Patient Eligibility

Eligibility criteria will be evaluated during screening and reasons for ineligibility will be extracted in the electronic case report form (eCRF).

8.2.3.1 Inclusion Criteria

- Adult (≥ 18 years) as of the index date
- KRAS p.G12C-mutated locally advanced or metastatic NSCLC
- Received at least 1 dose of sotorasib
- Receipt of at least 1 prior systemic therapy before use of sotorasib
- · Obtained ICF, if required

8.2.3.2 Exclusion Criteria

Documentation of being a non-Chinese ethnicity.

8.2.4 Matching

Not applicable

8.2.5 Baseline Period

The baseline period is defined as the period starting from diagnosis to the index date.

Data ranging from date of diagnosis of advanced NSCLC until the start of index therapy

Protocol Number: 20240175

Date: 27 March 2025 Page 21 of 47

will be extracted, including baseline demographics, clinical information, and treatments (see details in Section 8.3.3).

8.2.6 Study Follow-up

As the Hong Kong SAR CDARS database is a closed-loop database with linkage to the regional deaths registry, patients without evidence of death in the CDARS database by the data cut-off date were considered alive, and their last activity date will be the same as the cut-off date.

For the objective of OS, follow-up per patient will continue through earliest date of last clinical activity in the data source, data cut-off in the data source, or death.

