- Last treatment with sotorasib + 30 days

As the Hong Kong SAR CDARS database is a closed-loop database with linkage to the regional deaths registry, patients without evidence of death in the CDARS database by the data cut-off date were considered alive, and their last activity date will be the same as the cut-off date.

For objective of OS, follow-up per patient will continue through earliest date of last clinical activity in the data source, data cut-off in the data source, or death.

Variables

Outcomes:

- Primary: The patient incidence of AEs after sotorasib initiation.
- Secondary: OS from clinician notes in electronic health record and linkage to mortality records (where available).
- Exploratory: CCI

 CCI

Exposure:

o Use of sotorasib

Protocol Number: 20240175

Date: 27 March 2025 **Page 14 of 47**

Covariates

Key demographic, clinical characteristics, and pathology covariates including and not limited to age, sex, smoking status, body mass index (BMI), Eastern Cooperative Oncology Group (ECOG) performance status, histology, tumor stage, programmed death-ligand 1 (PD-L1) protein expression, presence of tumor mutations or rearrangements, laboratory test, electrocardiogram (ECG) and radiology, prior systemic treatments, brain metastases (if information available), prior lines of systemic therapy, and concomitant medications.

Study Sample Size

By the time of data cut-off, an estimated about 100 and 15 patients will have been treated with sotorasib and eligible for study inclusion from BOAO Pilot Zone and Hong Kong SAR, respectively. For a sample size of 115 patients and the observation of a proportion of 50% patients with an endpoint the largest level of margin of error (indicating the lowest level of precision) is \pm 9.14%.

Data Analysis

Frequencies will be presented for categorical demographic, clinical, and pathological variables. Descriptive statistics (mean, median, standard deviation, and range) will be presented for continuous variables.

The patient incidence of AEs will be summarized by count and proportions, specifically the proportion of patients experiencing AEs relative to the total number of patients. Median OS and PFS, along with the corresponding 95% confidence intervals (CIs) will be calculated using Kaplan-Meier estimates. The estimated survival probabilities, along with the corresponding 95% CIs will be presented for patients at 6 and 12 months.

CC

5. Amendments and Updates

None

6. Rationale and Background

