8.2.1 Study Period

The study eligibility period extends from the patients' index date (ie, the initiation of sotorasib) to the end of study period, defined as the earliest occurrence of patient's last activity date in the data source, data cut-off date or death.

The first available sotorasib use in BOAO Pilot Zone is around August 2021 through a pre-registration program. Specifically, sotorasib was included in the following hospitals'

Protocol Number: 20240175

Date: 27 March 2025 **Page 20 of 47**

drug lists and available for prescription: Ruijin Hainan Hospital in July 2022; BOAO Super Hospital in August 2021; BOAO Hengda Hospital in November 2021; and BOAO future Hospital in January 2022. The data cut-off will be the EC submission date (~ Q2 2025).

Sotorasib was approved in Hong Kong on April 29, 2022. The eligible treatment should occur after April 29, 2022. The data cut-off will be the date of data extraction (~ Q3 2025).

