8.3.2 Outcome Assessment

Safety Outcomes

In BOAO Pilot Zone, the AEs recorded in the electronic health record database throughout the study period will be documented and analyzed. Detailed information in medical records including vital signs, concomitant treatments, results of routine laboratory testing, ECG, and radiology will be reviewed to verify these AEs. Severity grade of AEs will be further verified by investigators according to the Common Terminology Criteria for Adverse Events (CTCAE), version 5.0 (CTCAE v5.0).

The patient incidence of AE after sotorasib initiation, including:

- TEAE
- Adverse event of interest, inclusive of hepatotoxicity, interstitial lung disease/pneumonitis, and renal toxicity
- Treatment-related AEs
- Treatment-related AEs of grade 3 or worse
- Serious treatment-related AEs
- Treatment-related AEs leading to treatment discontinuation
- Treatment-related AEs leading to dose reduction
- Treatment-related AEs leading to death

[figure not shown]
In Hong Kong SAR CDARS database, only adverse event of interest, inclusive of hepatotoxicity, interstitial lung disease/pneumonitis, and renal toxicity will be documented and analyzed. Each event of interest is a grouping of individual preferred terms determined using the following standardized MedDRA queries (SMQs): drug-related hepatic disorders – comprehensive search (SMQ narrow) for hepatotoxicity; interstitial lung disease (SMQ narrow) for ILD/pneumonitis; and acute renal failure (SMQ narrow) for renal toxicity. Medical records including diagnosis, vital signs, concomitant treatments, results of routine laboratory testing, ECG, and radiology will be reviewed to identify and verify AE. Detailed testing and exams to review will be further clarified in the statistical analysis plan and eCRF.

Protocol Number: 20240175

Date: 27 March 2025 Page 23 of 47

OS

• OS: The time from the index date to death from any cause. Patients without evidence of death at data cutoff will be right-censored at their last activity date.

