8.7.2.2 Missing or Incomplete Data and Lost to Follow-up

This is a retrospective chart review study. Information which is not included in the patient medical charts cannot be reported. Missing data will not be replaced by imputation methods. All analyses will be conducted in patients with available information.

As described in Section 8.4, during the treatment period, physicians proactively follow up with patients in BOAO Pilot Zone. In addition, as advanced NSCLC is a life-threating disease which needs close support from physicians specialized in treating NSCLC, it is expected that patients remain at same site for treatment.

Outcome assessment up to the end of follow-up defined in Section 8.2.6 will be included in the analysis.

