8.9.3 Analysis Limitations

CCI
We will perform a sensitivity analysis in which patients who
switch to other commercially available drugs or clinical trial medications will be censored
for sotorasib treatment.
Estimates of OS are likely to be immature in this study due to the potentially short
observation period for some patients. Patients without evidence of death by the data
cut-off will be censored at their last confirmed activity date, potentially underestimating
the true time at risk. A sensitivity analysis will follow these patients to the end of the
study instead of censoring them at their last confirmed activity date.
CCI

Protocol Number: 20240175

Date: 27 March 2025 Page 35 of 47

No further analysis limitations are expected.

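### The protocol gives two incompatible rules for which deaths count in overall survival; programmed literally, the follow-up rule would censor known deaths and push OS upward

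*Protocol*

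**What the plan says.** Two sets of passages govern the OS endpoint.

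**The follow-up rule.** Protocol 8.2.6 says that for OS "follow-up per patient will continue through earliest date of last clinical activity in the data source, data cut-off in the data source, or death". The abstract (Section 4, Follow-up) has the same sentence, beginning "For objective of OS, follow-up per patient will continue through earliest date of last clinical activity in the data source". Section 8.2.1 closes the study period the same way, "defined as the earliest occurrence of patient's last activity date in the data source, data cut-off date or death". Section 8.7.2.2 then carries the limit into the analysis: "Outcome assessment up to the end of follow-up defined in Section 8.2.6 will be included in the analysis".

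**The endpoint rule.** Section 8.3.2 defines OS as "The time from the index date to death from any cause" and adds: "Patients without evidence of death at data cutoff will be right-censored at their last activity date". Section 8.9.3 repeats that it is patients without evidence of death who are censored at last activity.

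**Hong Kong.** For patients with no death on record, 8.2.6 says that "their last activity date will be the same as the cut-off date". It does not say how last activity relates to death for patients who died.

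The protocol does not define last clinical activity. It does not say whether a reported death, or a contact away from the BOAO hospital, counts.

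**The concern.** Clinical activity normally comes before death. If the end of follow-up is the earliest of the two dates, it is the last activity, and a later death falls outside the window even when its date is known. Section 8.7.2.2 would then keep that death out of the analysis. The patient becomes a censored observation shortly before dying, which is informative censoring.

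The BOAO setting makes such deaths plausible. Section 8.4 describes patients who often live elsewhere in mainland China and return monthly at first, then every 3 months. Sections 8.7.2.5.3 and 8.9.1.1 say BOAO deaths are reported deaths with no registry behind them.

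At stake are the event count, the Kaplan-Meier median and the 6- and 12-month survival estimates for the only secondary endpoint. The planned sensitivity analyses would not restore the lost deaths. The one in 8.9.3 extends follow-up only for patients without evidence of death. The one in 8.7.2.5.3 removes patients whose last activity precedes cut-off. Both 8.7.2.5.3 and 8.9.1.1 also tell the reader that survival is probably underestimated, which is the opposite of what the literal follow-up rule would produce.

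**Working it through.** **1. The plan's own figures.** The protocol states no OS calculation to reproduce. Its only design calculation is the margin of error in 8.5: sqrt(0.5 × 0.5 × 1.96² / 115) = 9.14%, as stated. This point does not depend on it.

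**2. One patient under both rules.** Take a patient last seen in January who dies in March, with the death reported before cut-off.
- Under 8.3.2 and 8.9.3 there is evidence of death by cut-off, so this is an event in March.
- Under 8.2.6 with 8.7.2.2 the earliest of January, March and cut-off is January, so the March death is outside follow-up and the patient is censored in January.

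The results agree only if the death report itself counts as clinical activity, which the protocol does not say.

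**3. Illustrative size.** Inputs from the protocol:
- Median OS of 10.6 months (95% CI 8.9-14.0), the phase III figure in Section 4.
- Visits monthly and then every 3 months (8.4), taken as months 0, 1, 2, 3 and every 3 months after that.
- First BOAO use in August 2021 and cut-off around Q2 2025, hence up to about 46 months of potential follow-up.

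Assumptions: exponential OS, potential follow-up uniform on 0-46 months, and a share q of deaths dated after the last activity. The documents do not give q.

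A first approximation: the monthly hazard is ln 2 / 10.6 = 0.0654. If a share q of deaths is lost, the event hazard falls to (1 − q) × 0.0654 and the median becomes about 10.6 / (1 − q). That is 11.8, 14.1 and 21.2 months at q = 10%, 25% and 50%.

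A simulation of 200,000 patients, with the affected patients censored at their last visit, gives somewhat lower medians because these patients also leave the risk set early:

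| Rule | KM median (months) | 6-month OS | 12-month OS | Deaths counted per 100 patients |
|---|---|---|---|---|
| Benchmark: living censored at cut-off | 10.6 | 67.6% | 45.7% | 68 |
| 8.3.2: all recorded deaths count, living censored at last visit | 10.3 | 67.0% | 44.6% | 68 |
| 8.2.6 literal, q = 10% | 11.3 | 69.6% | 48.1% | 62 |
| 8.2.6 literal, q = 25% | 13.4 | 73.6% | 53.8% | 51 |
| 8.2.6 literal, q = 50% | 19.6 | 81.2% | 65.7% | 34 |

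The exact exponential values are 2^(−6/10.6) = 67.5% and 2^(−12/10.6) = 45.6%, which the benchmark row matches.

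**4. Range over the true median.** With q = 25%, a true median of 8.9 months becomes 11.1, and one of 14.0 becomes 17.6.

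**5. Direction.** The literal rule can only remove events that 8.3.2 counts. In the simulated cases this raises the curve, and at q = 10% it already exceeds the true value. As q approaches zero the literal rule approaches the 8.3.2 result of 10.3 months, slightly below the truth because the living are censored at their last visit.

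**The case against.** The strongest reply is that the endpoint itself is defined properly. Sections 8.3.2 and 8.9.3 are the passages that say who is an event and who is censored, and the objectives table in Section 4 also runs OS to the date of death. On this view 8.2.6 only describes an observation window and does not tell anyone to recode a known death. A strict minimum would also be odd: with no activity after death, the death term would almost never bind, and only deaths on a day of recorded contact would count. The likely intent is therefore the 8.3.2 rule. This argument stands as a reading of intent. It does not remove the conflict, because 8.7.2.2 applies the 8.2.6 window to the analysis.

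A second reply also has force. Last clinical activity might be read broadly. Section 6.3 says BOAO physicians document follow-up both inside and outside the zone, so the last activity may be close to death, and a recorded death report might itself qualify. That would shrink or close the gap, but the protocol does not settle it.

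A reader might go further and infer that OS is overstated under this plan, in both regions, by a large amount. The documents do not support that. Exclusion of these deaths is not settled, the share affected is unknown, and Hong Kong is about 15 patients with registry linkage and a stated expectation of complete OS follow-up.

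**Conclusion.** The protocol contradicts itself on which deaths count for OS. Sections 4 (Follow-up), 8.2.1, 8.2.6 and 8.7.2.2 point one way, and 8.3.2 and 8.9.3 the other.

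The upward bias is conditional: it arises if the follow-up rule is programmed literally and a death report is not treated as clinical activity. It would then fall mainly on BOAO. Under the assumptions shown, 12-month OS would read about 48%, 54% or 66% for q of 10%, 25% or 50%, against a true 46%. These sizes are illustrations, since q, the exponential shape and the visit pattern are assumed. If 8.3.2 is followed, the overstatement does not occur.

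This should be fixed before programming. It is a drafting conflict in a descriptive secondary endpoint whose intent can probably be read, and it does not show that the planned OS estimate is wrong.

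**What to change.** Align Section 4 (Follow-up), 8.2.1, 8.2.6 and 8.7.2.2 with 8.3.2. Suggested content for OS:

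- Any recorded death, reported or from the registry, dated on or before data cut-off is an event on its date, whatever the date of last clinical activity.
- Last activity is the censoring date only for patients without a recorded death. For Hong Kong that date remains the cut-off.
- For BOAO, last clinical activity means the last date the patient is known to be alive, including documented remote or off-site contacts.

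Section 8.7.2.2 should say that, for OS, deaths are included under this rule. The cost is a few sentences in four places and one definition. No new data source is needed. The sponsor should check that the eCRF holds the date of death and the date last known alive as separate items.

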8.3 Variables

8.3.1 Exposure Assessment

The exposure variable is receipt of sotorasib. Patients will be considered as exposed from time of their initial date of sotorasib administration through treatment discontinuation. If the status of treatment is unclear at the end of the study, the last date of treatment will be considered as either the date of the last prescription in the database plus the corresponding dosing time from that prescription, or the end of the study, whichever occurs earlier. Treatment information of sotorasib will be extracted through follow-up. Detailed sotorasib treatment information to be extracted include:

- Treatment initiation date
- Treatment duration
- Dose and dosing schedule
- Dose reduction and modification, including dates and reasons.
- Treatment interruption, time interval from interruption to re-initiation, and subsequent re-initiation of treatment (if any)

Protocol Number: 20240175

Date: 27 March 2025 Page 22 of 47

Treatment discontinuation, including date and reason (if any)

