In BOAO Pilot Zone, patients, often residing from across mainland China, need to be physically admitted to one of the several hospitals in BOAO Pilot Zone to receive sotorasib. The first hospitalization includes a complete medical history, radiology scans, tumor biomarker assessment, and liver and renal function tests to inform clinicians' decision to treat. As sotorasib is in the pre-registration program, the government requires close monitoring and reporting of safety events, which are well documented in the established hospital system. Hence, expectation that safety endpoints will be measured adequately in this study. As sotorasib is an oral medication taken daily until disease progression or unacceptable toxicity, patients need to physically return to the BOAO Pilot Zone hospital at least once per month initially, and every 3 months thereafter, to continue therapy. A case report form created for this study will be used to extract the relevant structured and unstructured data from the electronic heath record.

In Hong Kong SAR, the Clinical Data Analysis and Reporting System (CDARS) database will be used to identify patients treated with sotorasib at any public hospital. CDARS is a population-based database covering residents in Hong Kong SAR and can be linked to mortality records. Hence, the expectation that OS will be measured with complete follow-up. While the structure data within CDARS will provide most of the relevant data for study, the unstructured clinical notes within the electronic health record (Electronic Patient Record/Clinical Management System [EPR/CMS]) will also be used to augment information on key covariates.

Summary of Patient Eligibility Criteria

Inclusion Criteria:

- Adult (≥ 18 years) as of the index date.
- KRAS p.G12C-mutated locally advanced or metastatic NSCLC
- Received at least 1 dose of sotorasib.
- Receipt of at least 1 prior systemic therapy before use of sotorasib
- Obtained informed consent form (ICF), if required.

Exclusion Criteria:

Documentation of being a non-Chinese ethnicity.

Protocol Number: 20240175

Date: 27 March 2025 **Page 13 of 47**

Follow-up

Index date: sotorasib initiation date.

For objective of safety, CC

follow-up per patient

will continue through earliest date of:

- Last clinical activity in the data source
- Data cut-off in the data source:
 - BOAO Pilot Zone: Ethics Committee (EC) submission date
 (~ Q2 2025)
 - Hong Kong SAR: Data extraction cut-off date (~ Q3 2025)
- Death

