8.4 Data Sources

In BOAO Pilot Zone, patients, often residing from across mainland China, need to be physically admitted to one of the several hospitals in BOAO Pilot Zone to receive sotorasib. The first hospitalization includes a complete medical history, radiology scans, tumor biomarker assessment, and liver and renal function tests to inform clinicians' decision to treat. As sotorasib is in the pre-registration program, the government requires close monitoring and reporting of safety events, which are well documented in the established hospital system. Hence, expectation that safety endpoints will be measured adequately in this study. As sotorasib is an oral medication taken daily until disease progression or unacceptable toxicity, patients need to physically return to the BOAO Pilot Zone hospital at least once per month initially, and every 3 months thereafter based on physician's assessment and justification, to continue therapy. Patients seeking refills require recent radiology results, organ function evaluation etc. reassessment. Refills can be initiated with online evaluations and subsequently processed through outpatient clinics at hospitals in Hainan. Reports from Tier A hospitals across China are accepted. A case report form created for this study will be used to extract the relevant structured and unstructured data from the electronic heath record.

In Hong Kong SAR, this study will be using the electronic health records of the CDARS database managed by the Hong Kong Hospital Authority, a statutory body in charge of all public hospitals and their ambulatory clinics in Hong Kong SAR. Anonymized patient data are transferred daily to CDARS for audit purposes from the clinical management system (CMS) of the Hospital Authority, which contains medical records including: demographic information, diagnoses, prescription records, laboratory tests, accident and emergency attendance, outpatient clinics, hospital stay, and discharge information of patients since 1993. It also contains data on causes of death through its internal linkage

Protocol Number: 20240175

Date: 27 March 2025 Page 26 of 47

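### The safety window does not stop at the next anticancer therapy, so TEAE and AE-of-interest incidences can include events of the next regimen

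*Protocol*

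**What the plan says.** **Follow-up rule (Section 4, Follow-up).** Safety follow-up ends at the earliest of four dates: "Last clinical activity in the data source", the regional data cut-off, death, and "Last treatment with sotorasib + 30 days". No stop refers to a later anticancer therapy. Part of the lead-in is blacked out.

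**Exposure (Section 8.3.1).** The default is: "Patients will be considered as exposed from time of their initial date of sotorasib administration through treatment discontinuation". Discontinuation date and reason are extracted. A fallback applies under one condition, "If the status of treatment is unclear at the end of the study". Then "the last date of treatment will be considered as either the date of the last prescription in the database plus the corresponding dosing time", or the end of the study if that comes first.

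**Outcomes (Section 8.3.2).** BOAO has eight AE endpoints. Six are limited to treatment-related AEs; TEAEs and AEs of interest (hepatotoxicity, ILD/pneumonitis, renal toxicity) are not. Hong Kong analyses only the AEs of interest. BOAO AEs are taken from the whole study period, which Section 8.2.1 ends at last activity, cut-off or death, with no 30-day limit.

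**Switching (Section 8.9.3).** A sensitivity analysis is planned in which patients who "switch to other commercially available drugs or clinical trial medications will be censored" for sotorasib treatment. The text just before it is blacked out, so the endpoint it serves cannot be seen.

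**Hong Kong activity date (Sections 4 and 8.2.6).** A patient with no recorded death is given a last activity date equal to the cut-off.

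**The concern.** The primary objective is the safety profile of sotorasib. For an endpoint that counts any qualifying event in a window, the window decides what is attributed to the drug. A patient who stops sotorasib and starts another regimen within 30 days remains in the sotorasib window while being treated with something else. A hepatic, pulmonary or renal event that begins then is counted, and no relatedness judgement removes it.

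The next regimen need not be benign. Section 6.1 names docetaxel among the usual second-line or later treatments. The phase III figures in Section 6.2 give grade 3 or worse events in 40% on docetaxel against 33% on sotorasib, and serious treatment-related AEs in 23% against 11%. These rates are not specific to the AEs of interest, but they show that the overlap can carry events.

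At stake are the BOAO TEAE and AE-of-interest incidences and the whole of the Hong Kong safety result.

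**Working it through.** **1. The plan's own precision figure.** Section 8.5 uses e = 1.96 × √(p(1−p)/n). At p = 50%, n = 115: 1.96 × √(0.25/115) = 9.14%, as stated. The other four rows of Table 1 also reproduce (8.95, 8.38, 7.31 and 5.48%). None depends on the safety window. The protocol gives no figure for contamination of that window.

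**2. Which stop ends the window after a switch?**
- *BOAO, discontinuation date known:* 30 days after the actual stop, unless last activity, cut-off or death is earlier.
- *BOAO, status unclear:* 30 days after the fallback date, but still no later than last activity. A patient who leaves with nothing further on file is cut off there. The longer tail matters only if later contacts are recorded. Section 6.3 says physicians document evaluations both inside and outside BOAO, so this can happen.
- *Hong Kong, no recorded death:* last activity equals cut-off, so only the 30-day stop can end the window before cut-off.

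**3. Length of the tail.** With a known stop it is up to 30 days. Under the fallback it is unused supply + 30 days. The protocol gives no supply length. Section 8.4 gives only a BOAO return interval, "at least once per month initially, and every 3 months thereafter". Assuming a supply of 30 or 90 days:

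| Assumed supply | All used | Half used | None used |
|---|---|---|---|
| 30 days | 30 days | 45 days | 60 days |
| 90 days | 30 days | 75 days | 120 days |

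**4. Effect of one patient.** Section 8.7.2.1 analyses the regions separately. One misassigned patient adds 1/15 = 6.7 points in Hong Kong and 1/100 = 1 point in BOAO.

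**5. Illustration for an unfiltered endpoint.** Let p0 be the incidence on sotorasib, s the share starting another therapy inside the window, and r the risk of a qualifying event from that therapy during the overlap. Added incidence = (1−p0) × s × r. All three inputs are assumptions.

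| p0 | s | r | Added | Observed | Margin of error, n = 100 |
|---|---|---|---|---|---|
| 10% | 20% | 5% | 0.90 × 0.20 × 0.05 = 0.9 points | 10.9% | 5.88 points |
| 10% | 60% | 20% | 0.90 × 0.60 × 0.20 = 10.8 points | 20.8% | 5.88 points |
| 20% | 20% | 5% | 0.80 × 0.20 × 0.05 = 0.8 points | 20.8% | 7.84 points |
| 20% | 60% | 20% | 0.80 × 0.60 × 0.20 = 9.6 points | 29.6% | 7.84 points |

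The range runs from negligible to larger than the sampling error. The upper end needs both frequent early switching and a high event risk in a short overlap.

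**The case against.** The strongest defence is that a window of last treatment plus 30 days is a legitimate choice: it keeps delayed sotorasib events, which a stop at the switch would drop. Section 8.9.3 also shows that switching was considered, Section 8.7.2.1 leaves detail to an analysis plan not shown here, and some follow-up text is blacked out. The point about delayed events stands, and is why the present window should be kept as a second summary. The rest does not answer the concern: the visible rule lists its stops explicitly, and the switch analysis is a sensitivity analysis whose endpoint is hidden.

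Stronger readings are tempting, but the documents do not support them:

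- *That the supply-based date is the general rule.* It applies only when status is unclear; otherwise the discontinuation date governs.
- *That BOAO patients stay exposed for months after going home.* The last-activity stop cuts off anyone with no later record. Section 6.3 expects outside evaluations, safety events and discontinuation to be documented, so an event recorded without the stop should be the exception.
- *That prescriptions cover three months.* Section 8.4 gives a visit interval, not a supply length.
- *That the off-drug share of the window measures the bias.* Taking the phase III median PFS of 5.6 months as time on drug, the shares are 1/6.6 = 15% for the 30-day tail, 2.5/8.1 = 31% with half of a three-month supply unused, and 4/9.6 = 42% with all of it unused. These are shares of time off sotorasib. They are neither time on another regimen nor added incidence.
- *That all reported sotorasib toxicity is inflated.* Six of the eight BOAO endpoints require relatedness. Next-regimen events enter those only through misattribution, although Section 6.3 concedes that relationship may be unconfirmable for some patients.

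**Conclusion.** The point holds within limits. No visible main-analysis rule ends the safety window at the start of a subsequent anticancer therapy. TEAEs in BOAO and AEs of interest in both regions can therefore include events of the next regimen, and their incidences can be overstated. The fallback date can widen the gap even when a switch is on record; last activity limits this in BOAO but not for Hong Kong patients without a recorded death.

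The size cannot be derived from the protocol, which gives neither the share who switch within the window nor the event risk on the next regimen. The figure of 0.8 to 10.8 points rests on assumed inputs (incidence 10 to 20%, switching 20 to 60%, event risk 5 to 20%). The 6.7 points per Hong Kong patient follow from the expected 15 patients alone.

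Separately, Sections 8.2.1 and 8.3.2 describe a longer BOAO AE window than the abstract. As they stand, the two cannot both define the analysis. This is a worthwhile and inexpensive improvement; it does not affect the sample size or Table 1.

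**What to change.** 1. In the safety follow-up rule, for TEAEs and AEs of interest, add the start of a subsequent systemic anticancer therapy as a stop. Define it as a switch, not a drug given in combination with sotorasib, since Section 8.3.3 allows for combination use. Report the present window (last treatment plus 30 days) alongside, so that late sotorasib events stay visible.
2. In the unclear-status rule of Section 8.3.1, cap the last treatment date at the day before a documented switch.
3. Reconcile the whole-study-period AE capture in Sections 8.2.1 and 8.3.2 with the 30-day limit in the abstract, so that one window governs the analysis.

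**Cost.** Some wording, one additional date comparison and a second summary table. Switch dates are already needed for the analysis in Section 8.9.3. A late sotorasib event after a switch would appear only in the second table, and undocumented switches would remain uncorrected.
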